4.0 STUDY MODALITIES

4.1 Imiquimod

4.1.1 Packaging, labelling, and storage

Medication numbers will be unique to each box and will be used for tracking purposes only.

4.1.2 Imiquimod

Imiquimod will be supplied as vaginal suppositories. Available dosage strengths will be 6.25mg and 3.125 mg. Suppositories will be supplied in boxes.

Handling instructions will include washing hands before and after vaginal suppository is placed. Subjects will be advised not to have sexual intercourse during the nights in which they applied vaginal suppositories and to perform a vaginal douche in the morning. Subjects will be instructed to suspend the application of vaginal suppositories during the first 3 days of their menses. In addition, subjects may use a tampon following insertion to keep the suppository in place and apply Vaseline to skin surrounding the insertion area to prevent irritation. A 24-hour phone number is provided should subjects have any issues or concerns.

HIC#: 1603017415 Protocol version 11.0

CIN 2/3

Boxes will be labelled according to local regulations and will include the following as a minimum:

- Study number.
- Product name (Imiquimod)
- Contents of the boxes (18 and 24 vaginal suppositories)
- Suppository strength (mg)
- Batch number
- Medication number
- Use-by date
- Storage information
- Instructions for use
- Sponsor name and address
- A statement that the medication is for clinical study use only
- A caution statement

A new box of medication will be dispensed on day 1 (day of enrollment). The subject will initially receive one box of 6.25 mg tablets and in the event that dose reduction is necessary the subject will return to the clinic and new medication will be dispensed.

4.1.3 Storage conditions

Imiquimod must be stored refrigerated in the original package. Suppositories must be stored according to label instructions.

4.1.4 Drug accountability

Drug supplies, which will be purchased from Apex Pharmacy (Hamden, CT), will be kept in a secure, limited access storage area under the storage conditions. Where necessary, a temperature log must be maintained to make certain that the drug supplies are stored at the correct temperature.

The responsible person must maintain records of the product's delivery to the study site, the inventory at the site, the use by each subject, and the return to Apex Pharmacy or alternative disposition of unused product(s).

These records will include dates, quantities, batch/serial numbers, expiry ('use by') dates, and the unique code numbers assigned to the investigational product(s) and study subjects. The responsible person will maintain records that document adequately that the subjects were provided the doses specified by the CSP

HIC#: 1603017415 Protocol version 11.0

CIN 2/3 7

and reconcile all investigational product(s) received from Apex Pharmacy. The responsible person must verify that all unused or partially used drug supplies have been returned by the clinical study subject.

4.2 9-valent Human Papillomavirus Vaccine (Gardasil 9)

4.2.1 Packaging, labelling, and storage

Commercially available vaccine (GARDASIL®9- Merck) will be purchased by the Investigational Drug Service at Yale New Haven Hospital and stored under appropriate conditions in its original container until dispensed to study participants.

4.2.2 9-valent Human Papillomavirus Vaccine

9-valent HPV vaccine will be administered in the clinic by a nurse. The vaccine will be supplied in single-dose vials and is administered as 0.5 mL per dose intramuscularly in the deltoid region of the upper arm or in the anterolateral area of the thigh. Thorough agitation immediately prior to administration is necessary to maintain suspension of the vaccine.

Subjects randomized to the Imiquimod + HPV vaccine arm of the study will receive a dose of the vaccine on day 1 (day of enrollment). Subjects meeting criteria for a booster dose will return to the clinic to receive a second dose of the vaccine in week 8.

4.2.3 Storage conditions

HPV vaccine must be stored in the original package to protect from light and refrigerated at 2°C to 8°C (not to be frozen) and administered as soon as possible after being removed from refrigeration.

4.2.4 Drug accountability

9-valent HPV vaccine will be supplied, stored, and maintained by Yale-New Haven Hospital's Investigational Pharmacy (oversight by [name]). Per their protocol, the vaccine supply will be kept in a secure, limited access refrigerated storage area under the storage conditions. A temperature log must be maintained to make certain that the drug supplies are stored at the correct temperature.

The responsible person must maintain records of the product's delivery to the study site, the inventory at the site, the use by each subject, and the return to YNHH Investigational Pharmacy or alternative disposition of unused product(s).

These records will include dates, quantities, and batch/serial numbers, expiry ('use by') dates. The responsible person will maintain records that document adequately that the subjects were provided the doses specified by the CSP and reconcile all product(s) received from YNHH Investigational Pharmacy. The responsible person must verify that all unused or partially used drug supplies have been returned by the clinical study subject.

5.0 CORRELATIVE STUDIES

5.1 Histopathology: Cervical biopsies will be collected at the time of initial colposcopic evaluation based on clinical guidelines for management of abnormal pap tests. Cervical biopsies will be processed

HIC#: 1603017415 Protocol version 11.0

in the surgical pathology department. Cervical biopsies with high-grade (CIN 2/3) dysplasia will be centrally reviewed and diagnosis confirmed by study pathologists, in the Pathology Department at Yale University. Subjects with confirmed CIN 2/3 are eligible for enrollment. Colposcopy will be performed and cervical biopsies collected during weeks 20-24 (4-8 weeks after completion of Imiquimod therapy) will be centrally reviewed in the Pathology Department at Yale University to assess for the primary outcome. Pathologists will be blinded to study randomization.

5.2 HPV DNA Testing & HPV 16/18 Genotyping: Confirmatory high-risk HPV DNA testing will be performed under supervision of cytopathologist [name] in the Pathology Department at Yale University from cervical cytobrush sample obtained on day of enrollment. HPV 16/18 genotyping will be performed via PCR from cervical cytobrush sample by [name] Lab to establish baseline HPV status. This testing will be repeated between weeks 16-18 from cervical cytobrush samples and at final study visit during weeks 20-24 or following at least 3 weeks after completion of imiquimod therapy.

5.3 Exploratory Objectives

- 5.3.1 In the translational research component of this study we are planning to systematically evaluate and compare T cell infiltration into the cervical dysplasia and correlate with clinical response. The ultimate goal being to determine if the prime and pull strategy of Imiquimod + HPV vaccine leads to the establishment of T_{RM} cells and if this correlates to clinical regression of high-grade cervical dysplasia. The pre- and post-treatment cervical biopsies will be examined to determine the frequencies and anatomical distributions of CD4 and CD8 T cells within the CIN. We will stain paraffin embedded tissue sections with antibodies to CD4 and CD8. These sections will be costained with well-established markers of human T_{RM} (CD69, CD103).³¹ The comparison of T_{RM} frequencies and distributions will be conducted both within the individual (pre and post prime and pull) as well as amongst the groups at the relevant time points. We will assess possible correlation between T_{RM} and viral clearance and clinical outcomes. Because the biopsy sample is quite limited in size, we will also collect cells from the endocervical cytobrush to analyze the local T cell populations. The protocol for isolating and analyzing T cells from cytobrush is well established.³² We will stain the collected CD4 and CD8 T cells with respect to their T_{RM} (CD69, CD103) phenotype, as well as ex vivo stimulation with HPV peptide pool (the same one used in the CFSE experiments briefly described below) and measuring TNF- α and IFN- γ secretion by intracellular staining.

6.0 TREATMENT PLAN AND ENTRY PROCEDURE/REGISTRATION PROCEDURE

HIC#: 1603017415 Protocol version 11.0

6.1 Study Entry: Subjects will be screened and consented by the P.I. or a member of the study staff. Consent may be obtained remotely. The consent form can be mailed or emailed to the research participant who will sign a printed version of the consent form and fax/scan/email/send a picture of the signed consent form or mail the signed consent form back to the researcher.

[figure not shown]

FIGURE 1: Study Timeline

6.2 Treatment Plan This is a randomized Phase II, three arm control trial in subjects with CIN 2/3 high grade cervical dysplasia. Subjects with CIN 2/3 meeting eligibility criteria will have cervical biopsy specimens centrally reviewed by study pathologist to confirm diagnosis. HPV DNA test and HPV 16/18 genotyping will be performed from endocervical cytobrush samples to determine HPV status associated with the dysplasia.

Subjects who have CIN 2/3 with HPV+ disease will be enrolled in this study. Subjects will be randomized to one of three arms: observation only (control), imiquimod only, imiquimod + 9-valent HPV vaccine. All cytology and cervical biopsy specimens related to the study will be centrally reviewed by study pathologists who will be blinded to treatment assignment.

6.2.1 Pre-Treatment Visit/Study Enrollment: After the index cervical biopsy demonstrating CIN 2-3, all subjects will be brought back to clinic to discuss results and management. After obtaining informed written consent the following pre-treatment tests will be performed: medical history, physical exam with pelvic exam, vital signs, urine pregnancy test (must be performed within 7 days of treatment), translational blood

HIC#: 1603017415 Protocol version 11.0

samples (may be drawn after randomization but must be drawn prior to treatment), endocervical specimen to be sent to Yale Pathology for high-risk HPV DNA testing (if high-risk HPV DNA results are already available, this testing may not have to be repeated) and a second endocervical cytobrush specimen for translational research purposes. Blood samples will be collected in sodium heparin tubes with about 28 cc collected each time as follows: 7 cc in each of 3 green top tubes and 7 cc in 1 EDTA/purple top tube (see follow up visits below). Endocervical specimen for high-risk HPV DNA test to be performed by Yale Pathology will be submitted in usual fashion as a SurePath specimen. Endocervical cytobrush sample for study purposes will be collected into a 50ml conical tubes containing PBS using sterile techniques and will be stored on ice until picked up by a laboratory personnel. Once all eligibility has been met the subject will be randomized to one of three arms.

Additional components of visit outline by study group:

- (1) Control group: Observation at specified study timepoints.
- (2) Imiquimod only: At the baseline visit, this group will receive instruction on imiquimod self application (16 week course) using a 6.25 mg vaginal suppository, storage of medication, possible side effects. Subjects will be provided a diary and case report form to record vaginal suppository application and side effects will be recorded per NCI Common Terminology Criteria for Adverse Events (CTCAE 4.0). Imiquimod self-application regimen will be similar to one previously described²⁴ and is as follows:
- Treatment weeks 1 and 2: Subjects apply one vaginal suppository per week
- Treatment weeks 3 and 4: Subjects apply two vaginal suppositories per week
- Treatment weeks 5 to 16: Subjects apply three vaginal suppositories per week

Vaginal suppositories will be self-applied by the subjects in the evening right after going to bed. Subjects will be advised not to have sexual intercourse during the nights in which they applied vaginal suppositories and to perform a vaginal douche in the morning. Subjects will be instructed to suspend the application of vaginal suppositories during the first 3 days of their menses. Subjects will be advised to keep the study medication refrigerated. In case of persistent side effects in subjects of the imiquimod group, the dose of the study medication will be modified and participants will receive vaginal suppositories containing only 50% of the original imiquimod dose (vaginal suppositories containing 3.125 mg imiquimod).

Missed doses of imiquimod can be made up the following day. Otherwise, the dose must be skipped and subjects should take the next scheduled dose at the usual time.

Imiquimod will be dispensed in boxes containing 18 vaginal suppositories (treatment weeks 1-8) at the beginning of the treatment course. During follow up visit at week 8 (see below), subjects will be provided a new box of 24 vaginal suppositories to complete treatment course for weeks 9-16. Study drug will be prescribed by the investigator and may be dispensed either by the investigator or study staff.

HIC#: 1603017415 Protocol version 11.0

CIN 2/3

11

(3) Imiquimod + HPV vaccine: At the baseline visit, this group will be instructed about the correct method of self-application of imiquimod 6.25mg as a vaginal suppository as described above, storage of medication, possible side effects. Subjects will be provided a diary and case report form to record vaginal suppository application and side effects will be recorded per NCI Common Terminology Criteria for Adverse Events (CTCAE 4.0). In addition, all women (regardless of age) will be administered a dose of the HPV vaccine on day of enrollment (regardless of previous HPV vaccination history). Women previously unvaccinated will receive an additional booster dose at 8 weeks. Local pain will be assessed with a visual analog scale immediately after vaccine administration and 5 minutes later. Subjects will be provided a separate case report form to record vaccine side effects per CTCAE 4.0.

Missed doses of imiquimod can be made up the following day. Subjects are encouraged to complete taking all prescribed doses. If additional time is required toward this goal of treatment, the scheduled dosing period may be extended.

Imiquimod will be dispensed in boxes containing 18 vaginal suppositories (treatment weeks 1-8) at the beginning of the treatment course. During follow up visit at week 8 (see below), subjects will be provided a new box of 24 vaginal suppositories to complete treatment course for weeks 9-16. Study drug will be prescribed by the investigator and may be dispensed either by the investigator or study staff.

6.2.2 Follow-up Visits: Follow-up visits will occur at week 8 (between weeks 7-9), at week 16 (between weeks 16-18) and once at week 22 (between weeks 20-24). For subjects randomized to treatment arms (2) Imiquimod only and (3) Imiquimod + HPV vaccine, the week 22 visit will occur at least 3 weeks after last dose of therapy. Urine pregnancy test will be performed at all follow-up visits. Subjects with exam findings concerning for worsening disease at any point in the study will be taken out of the study and treated with surgical excision procedure.

Week 8 (7-9 weeks) Visit: This visit will be timed to occur part way through the 16 week imiquimod treatment course. For women using imiquimod (Imiquimod only and Imiquimod + HPV vaccine arms), a review of medication diary, monitoring of correct use of study medication, and report of local and systemic side effects using a standardized case report form will occur at all follow up visits. For women who received HPV vaccine as part of study protocol (Imiquimod + HPV vaccine arm), a review of vaccination diary and report of local and systemic side effects using a standardized case report form will occur at all follow up visits. A pelvic exam with colposcopy will be performed to objectively assess for gross cervical lesions in all subjects and also for local side effects from imiquimod use in the Imiquimod only and Imiquimod + HPV vaccine arms. Endocervical cytobrush samples will be obtained at this time for study purposes. Cervical biopsies will be performed as clinically indicated. Blood sample collections will also occur. In addition, women in the Imiquimod + HPV vaccine groups who were previously unvaccinated will receive their booster dose of the HPV vaccine.

Week 16 (16-18 weeks) Visit: This visit will be timed to occur at completion of imiquimod treatment course. For women using imiquimod (Imiquimod only and Imiquimod + HPV vaccine

HIC#: 1603017415 Protocol version 11.0

CIN 2/3

arms), a review of medication diary, monitoring of correct use of study medication, and report of local and systemic side effects using a standardized case report form will occur at all follow up visits. For women who received HPV vaccine as part of study protocol (Imiquimod + HPV vaccine arm), a review of vaccination diary and report of local and systemic side effects using a standardized case report form will occur at all follow up visits. A pelvic exam will be performed to objectively assess for gross cervical lesions in all subjects and also for local side effects from imiquimod use in the Imiquimod only and Imiquimod + HPV vaccine arms. Endocervical cytobrush samples will be obtained at this time. HPV 16/18 genotyping will be performed using endocervical cytobrush samples at this time point. Colposcopy and cervical biopsies will be performed as clinically indicated. Blood sample collections will also occur.

Week 22 (20-24 weeks): This visit will be timed to occur at least 3 weeks after completion of imiquimod treatment course. For women using imiquimod (Imiquimod only and Imiquimod + HPV vaccine arms), a review of medication diary, monitoring of correct use of study medication, and report of local and systemic side effects using a standardized case report form will occur at all follow up visits. For women who received HPV vaccine as part of study protocol (Imiquimod + HPV vaccine arm), a review of vaccination diary and report of local and systemic side effects using a standardized case report form will occur at all follow up visits. A pelvic exam will be performed to objectively assess for gross cervical lesions in all subjects and also for local side effects from imiquimod use in the Imiquimod only and Imiquimod + HPV vaccine arms. Endocervical cytobrush samples will be obtained at this time. High risk HPV test and HPV 16/18 genotyping will be performed using endocervical cytobrush samples at this time point. Colposcopy and cervical biopsies will be performed on all subjects at this final study visit to assess primary endpoints. Blood sample collections will also occur.

Persistence of CIN 2-3 or worsening cervical dysplasia diagnosed at the 20-24 weeks visit will be recommended for treatment with surgical conization.

At approximately 3 months and 6 months after the last study visit, as per standard of care, it is recommended that subjects will have a pap smear with high-risk HPV testing. The results of this testing will be recorded in the subject's study record.

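### Section 6.2.1 gives the two imiquimod arms different rules for a dose not made up the next day: skip it in one arm, extend dosing in the other

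*Combined protocol and SAP*

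**What the plan says.** Section 6.2.1 sets out the imiquimod schedule under arm 2: one suppository a week in weeks 1-2, two a week in weeks 3-4, and then "Treatment weeks 5 to 16: Subjects apply three vaginal suppositories per week". Arm 3 refers back to this text for the method of application, and both arms receive a box of 18 followed by a box of 24.

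Each arm then has its own missed-dose paragraph. Both open by allowing a missed dose to be made up the next day. For a dose not made up then:

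- Arm 2: "Otherwise, the dose must be skipped and subjects should take the next scheduled dose at the usual time".
- Arm 3: "Subjects are encouraged to complete taking all prescribed doses", followed by "If additional time is required toward this goal of treatment, the scheduled dosing period may be extended".

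Section 6.2.2 names both imiquimod arms when it states that "the week 22 visit will occur at least 3 weeks after last dose of therapy". Sections 1.1 and 5.1 place the biopsy in weeks 20-24, 4 to 8 weeks after imiquimod ends. Section 7.3 counts suppositories at weeks 8 and 16 and takes back the remainder when the 16 weeks are over, with no distinction between arms. The per-protocol set in 15.2 requires that all doses of the assigned drug were received.

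**The concern.** Apart from the vaccine, arms 2 and 3 should be handled alike, because only the contrast between them bears on what the vaccine adds. Section 2.0 frames the rationale in those terms: prime and pull is expected to do better than imiquimod alone. A conduct rule that lets arm 3 recover doses which arm 2 must forgo adds a second difference between the arms.

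Three things can then diverge for reasons unrelated to the vaccine: the amount of imiquimod completed, the interval from last dose to biopsy, and eligibility for the per-protocol set. The first two also bear on the exploratory comparison of T-cell changes between groups (15.7), since section 2.0 describes imiquimod itself as inducing cytokines and activating T cells.

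**Working it through.** **Same regimen and supply.** Weeks 1-8: 2×1 + 2×2 + 4×3 = 18. Weeks 9-16: 8×3 = 24. Total 42, which matches the boxes of 18 and 24 in both arms. The difference is therefore confined to the missed-dose rule.

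**Does any text reconcile the rules?**

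- The back-reference in arm 3 covers how the suppository is applied. Arm 3 then gives its own missed-dose paragraph, so the skip rule is not imported.
- The 3-week rule in 6.2.2 names both arms. If dosing stops at week 16 and the visit is no earlier than week 20, the gap is at least 20 − 16 = 4 weeks. A 3-week minimum can bind only if the last dose falls after week 20 − 3 = 17. This suggests that late dosing was foreseen in arm 2 as well, but a visit-timing rule does not cancel an instruction to skip.
- Section 7.3 does not mention extension in either arm.

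**Exposure.** Suppose a subject misses m doses that are not made up the next day (m is an assumption; the documents give no rate). Arm 2 as written completes 42 − m. Arm 3 may complete 42. The shortfall is m/42: 0% for m = 0, 3/42 = 7% for m = 3, 4/42 = 10% for m = 4.

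**Timing.** Recovering k doses at three a week moves the last dose to week 16 + k/3. For a biopsy at week 22:

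| Doses recovered | Last dose (week) | Last dose to biopsy (weeks) |
|---|---|---|
| 0 | 16 | 6 |
| 3 | 17.0 | 5.0 |
| 4 | 17.3 | 4.7 |
| 6 | 18 | 4 |

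A few recovered doses keep the biopsy inside the planned 4 to 8 weeks. For a biopsy no later than week 24, a 4-week minimum puts the latest last dose at 24 − 4 = week 20, and a 3-week minimum at 24 − 3 = week 21. Section 6.2.1 states no cap.

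**Per-protocol set.** An arm 2 subject who skips a dose as instructed has not received all doses. An arm 3 subject who missed the same dose can still qualify by finishing later. Dose modification is listed in 15.2 as a deviation and excludes a subject in either arm, so the asymmetry concerns full-dose subjects who missed doses.

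**Planned tests.** Section 15.5 compares each active arm with control in the modified ITT set. No arm 3 versus arm 2 efficacy test is planned.

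**The case against.** The strongest reply is that this is a drafting mismatch with little consequence. The 3-week rule points to extension being meant for both arms. Arm 3's wording is permissive, so staff could skip there too. The week-16 visit has a 16-18 week window, so a short extension could end before the drug count: up to (18 − 16)×3 = 6 recovered doses would fit. Section 15.4 already tabulates dose received and treatment modifications by group, so unequal exposure would be visible. All of this stands and limits the point. It does not remove it, because staff who follow the text will treat the arms differently.

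Three stronger readings are tempting and are not supported:

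- A reader might infer that the primary results are biased. Each co-primary test compares one active arm with control, so a difference in handling between the two active arms does not invalidate either test.
- A reader might infer a fixed week-21 limit on extension. That is only one reading: 5.2 times the final visit "at final study visit during weeks 20-24 or following at least 3 weeks after completion of imiquimod therapy", and its alternative wording can be taken to allow a visit after week 24.
- A reader might infer from the menses instruction ("Subjects will be instructed to suspend the application of vaginal suppositories during the first 3 days of their menses") that most subjects will lose doses. The protocol sets a weekly number, with no weekdays or spacing. A 3-day pause leaves at least 7 − 3 = 4 days in a week for three doses, so no loss is forced. Nor does the plan say whether an instructed pause counts as a missed dose.

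**Conclusion.** The inconsistency is real: two different written rules for one imiquimod regimen, with no rationale and nothing elsewhere to reconcile them. It is probably an incomplete edit, which is an inference from 6.2.2 and not something the documents state. It should be corrected, but it does not threaten the primary analysis. Its reach is the informal comparison of arm 3 with arm 2, the exploratory between-group T-cell comparison, and a per-protocol analysis that is itself optional. The size cannot be given without a missed-dose rate; it is zero if doses are rarely missed beyond the next day, and it grows by 1/42 of the course for each such dose. The conclusion assumes that sites apply each paragraph as written to its own arm.

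**What to change.** Use one identical missed-dose paragraph for both imiquimod arms in 6.2.1: either skip in both or extension in both. Skip in both needs fewer edits.

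If extension is kept, state a last-dose cap that holds the biopsy within weeks 20-24 and at the chosen minimum interval (week 20 for 4 weeks, week 21 for 3 weeks). Amend 7.3 so that remaining drug is collected and counted at the end of dosing. The chosen interval must then read the same throughout: 1.1, 1.2.1 and 5.1 say 4 to 8 weeks; 5.2, 6.2.2 and 9.1 say at least 3; and 10.1 and 10.11 say 12 to 16 weeks after treatment ends.

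Under either option, state in 15.2 that a skip or pause instructed by the protocol does not by itself fail the all-doses condition, and report days from last dose to biopsy by arm in the 15.4 tables.

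The cost is short text edits and one table row, with no added subjects and no change to the primary test. Under extension, doses taken after the week-16 visit rest on the diary unless suppositories are also counted at week 22.

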7.3 Treatment compliance

The study medication will be given in accordance with the protocol and the instructions of the investigator.

The appropriate number of imiquimod suppositories for the first 8 weeks of imiquimod treatment course will be provided to subjects to be self-administered at home. At week 8 follow up visit, the appropriate number of imiquimod suppositories for weeks 9-16 imiquimod treatment course will be provided to subjects. Subjects will be asked to bring the remaining study medication at each follow-up visit (weeks 8, 16) to the investigator site for a compliance check. The remaining suppositories will be counted by the investigator/site staff and recorded at the investigator site. Discrepancies between the number of suppositories remaining and the calculated number the subjects should have used must be documented and explained. At the end of the 16-week period, any remaining medication will be collected.

The investigator can withdraw a subject from the study in the event of serious and persistent non-compliance which jeopardizes the subject's safety or render study results for this subject uninterpretable.

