15.2 Analysis Set Definitions

- **full analysis set**—all randomized subjects
- safety analysis set—all subjects who have received at least one dose of any study drug, and/or have had any assessments at baseline or later that could be associated with an AE; analyzed by treatment received
- ITT analysis set—all randomized subjects with valid baseline measurements; analyzed by treatment assigned
- modified ITT analysis set—all randomized subjects with valid baseline measurements, receiving at least one dose of any study drug, and have at least one valid post-baseline measurement of outcome; analyzed by treatment assigned

HIC#: 1603017415 Protocol version 11.0

- modified ITT completers analysis set—all randomized subjects who receive at least one dose of
 any study drug and have complete and valid post-baseline assessments of outcome; analyzed by
 treatment assigned
- **per protocol analysis set**—all randomized subjects who receive all doses of their assigned study drug, have complete and valid post-baseline assessments of outcome, and have no protocol deviations (e.g. dose modification, assessment outside of time window, non-compliance)

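### The first imiquimod box covers exactly weeks 1-8 while the resupply visit may fall in week 9, so a fully adherent woman seen within the window can be short by up to 3 of 42 doses, which arm (2) text gives her no clear way to recover

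*Combined protocol and SAP*

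**What the plan says.** Section 6.2.1 sets the imiquimod schedule in three steps. The first two weeks have a single weekly dose and the next two weeks have a pair; the last step reads "Treatment weeks 5 to 16: Subjects apply three vaginal suppositories per week".

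For supply, the same section says "Imiquimod will be dispensed in boxes containing 18 vaginal suppositories (treatment weeks 1-8) at the beginning of the treatment course". The resupply for weeks 9-16 is described this way: "During follow up visit at week 8 (see below), subjects will be provided a new box of 24 vaginal suppositories". The wording is repeated for arm (3). Section 4.1.2 says that each woman starts with one box, and the only other dispensing it describes is a return to clinic for a reduced strength. Section 7.3 agrees on the first supply: "The appropriate number of imiquimod suppositories for the first 8 weeks of imiquimod treatment course will be provided".

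On timing, section 6.2.2 says "Follow-up visits will occur at week 8 (between weeks 7-9"; the table in section 9.1 shows the same visit with a window of plus or minus one week.

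The missed-dose rules in section 6.2.1 differ by arm. Both allow a missed dose to be made up the following day. Beyond that, the arm (2) text has the dose skipped, whereas the arm (3) text encourages completion of every prescribed dose and permits a longer dosing period.

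The per protocol set in section 15.2 is restricted to "all randomized subjects who receive all doses of their assigned study drug", with further conditions that include no protocol deviations. Non-compliance is one of the listed examples of a deviation.

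**The concern.** The supply is sized to the nominal visit date and the visit is allowed a tolerance around that date. A box with no reserve works only if the visit happens before the first dose of week 9 is due. The plan permits a later visit and says nothing about how drug is to be provided until then.

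Two consequences follow. First, a woman and a site can both keep to the written rules and still have a treatment gap for an administrative reason. This can occur only in the imiquimod arms, and it affects the most adherent women, because those who skipped doses have some left over. Second, the gap can be treated differently in the two arms. Under the arm (2) text the doses may be lost. The woman would then not have received all doses and would fall outside the per protocol set although she complied. Under the arm (3) text she may finish the course late and remain in that set.

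The compliance check in section 7.3 compares the suppositories left with the number that should have been used. It provides no category for doses that could not be taken because none had been supplied.

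**Working it through.** **Inputs.** Weekly dose frequency, box sizes and the missed-dose rules come from section 6.2.1, the single initial box from section 4.1.2, and the visit window from sections 6.2.2 and 9.1.

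**Step 1: reproduce the box sizes.** Scheduled doses = sum over weeks of doses per week.

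- Weeks 1-8: 2 × 1 + 2 × 2 + 4 × 3 = 2 + 4 + 12 = 18. This matches the first box exactly.
- Weeks 9-16: 8 × 3 = 24. This matches the second box exactly.
- Whole course: 18 + 24 = 42.

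**Step 2: balance of the first box for a woman who takes every scheduled dose.** Balance = 18 − cumulative scheduled doses.

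| Resupply visit at end of | Doses scheduled by then | Balance |
|---|---|---|
| Week 7 | 15 | +3 |
| Week 8 | 18 | 0 |
| Week 9 | 21 | −3 |

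**Step 3: dependence on the visit day.** The plan does not define week 9 by day, so the shortfall is a range. As an illustration, assume that the three weekly doses fall on days 1, 3 and 5 of the week. Before day 1 of week 9 nothing is missing. By day 1 or 2 one dose has come due, by day 3 or 4 two, and by days 5 to 7 three. The range is 0 to 3 doses, and the maximum is 3/42 = 7.1% of the course. The next-day rule common to both arms can rescue at most the most recent of these doses.

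**Step 4: can the doses be recovered later?** Total supply remains 42, so no drug is missing over the course as a whole. A shift of one week would put the last dose at about week 17. The required minimum of 3 weeks before the final visit then gives 17 + 3 = week 20, which lies inside the 20-24 week window. Recovery is therefore feasible on the calendar. Whether it is allowed depends on the arm:

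- Arm (3): the text allows the dosing period to be lengthened, so all 42 doses can be taken.
- Arm (2): the text has a dose skipped if it is not made up the next day, so up to 3 doses can be lost.

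Section 7.3 adds that leftover medication is collected when the 16-week period ends, with no stated exception for extended dosing. That sits awkwardly with the arm (3) text.

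**Step 5: which analyses are touched?** Section 15.5 bases the main analysis on the modified ITT set, which for drug exposure requires only one dose of any study drug (section 15.2). A woman short by 3 doses stays in it. The per protocol set requires all doses, so she would leave it, but section 15.5 presents that analysis as one that may be provided.

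**The case against.** The strongest reply is that nothing here is a true contradiction. A window is a tolerance, and a visit in week 7 or 8 satisfies the box size, the window and the dosing schedule together. That stands. A reader might infer that the supply and window sections cannot both be followed, but the documents do not support this. They leave a gap at one end of the window and do not say how to close it.

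A second reply is that leftovers will often cover the gap. Dosing is suspended for the first 3 days of menses and may be paused for toxicity. This also stands in part: such women may not run out at all. It is not dependable, since a missed dose may be made up the next day and section 7.2.3.3 provides for postmenopausal participants.

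A third reply is that the drug is delayed rather than lost, because 42 suppositories are supplied in all. This holds for arm (3) under its extension text. It does not clearly hold for arm (2). A reader might also infer that the gap pulls both active arms toward control. The documents do not show that: arm (3) has a written way to recover the doses, and no effect of missing 0 to 3 doses on regression is given.

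Finally, section 7.3 already requires discrepancies to be documented and explained, and staff could dispense earlier since no section forbids it. Both are true. An explanation in the record is nevertheless not a defined category for analysis, and no section tells sites to resupply early.

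**Conclusion.** The point holds as a small gap between supply and visit timing. For a woman who has taken every scheduled dose and is seen in week 9, the first box can fall short by 0 to 3 suppositories, which is at most 7.1% of the course and at most about a week without drug. This assumes no leftovers and no resupply before the visit.

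The difference between the arms matters more than the size. Read as written, the same late visit can cost doses in arm (2) while arm (3) may recover them, and the affected arm (2) women can drop out of the per protocol set despite having complied. The effect on the main modified ITT comparison is probably small, because these women remain in that set and the maximum loss is modest.

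How many women would be affected cannot be estimated, since the documents give no distribution of visit dates within the window and no adherence figures. The change is worth making because it is cheap, not because the primary result is under threat.

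**What to change.** 1. Reconcile the first-box quantity (sections 4.1.2, 6.2.1 for arms (2) and (3), and 7.3) with the week 8 window (sections 6.2.2 and 9.1), so that no woman seen within the window can be without drug. On the present schedule, 21 doses fall due by the end of the window against 18 supplied. The sponsor decides whether the supply or the window changes; the dosing schedule is not in question.
2. Reconcile the missed-dose texts of arms (2) and (3) in section 6.2.1, and check them against the end-of-course collection of medication in section 7.3. Which rule applies is for the sponsor to decide.
3. In section 7.3, record doses missed for lack of supply separately from non-compliance, and state in section 15.2 how such women are classified for the per protocol set.

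The cost is a short amendment with matching pharmacy labelling, plus either a few suppositories per woman or a tighter visit window.
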